II	Fourteen (14) adults (18-65 years) of new-onset T1D diagnosed within last 6 months (\leq 180 days)																				
III	Fourteen (14) children (6-17 years) of established T1D of more than 6 months duration (>180 days) and up to 10 years																				
IV	Fourteen (14) children (6-17 years) of new-onset T1D diagnosed within last 6 months (\leq 180 days)																				
Drugs with route of administration	Dose	Arm A	Arm B																		
Ultra-refined omega-3 EPA/DHA concentrate in Liquid or	Based on the body weight of the participant Initial Dose:	Three times daily orally																			

	
Capsule formulations (ZoneLabs® OmegaRx®2 Fish Oil – Liquid; containing 3375 mg EPA+DHA [2250 mg EPA and 1125 mg DHA] in 5 mL
 
Of note, each 1 mL of OmegaRx®2 contains 675 mg of EPA+DHA.
	
150 mg of EPA+DHA per Kg body weight.
 
Maintaince Dose: Dose will be adjusted to maintain a target AA/EPA ratio of 1.5-3.0. AA/EPA ratios will be monitored monthly until achieving target levels and as per protocol or as clinically indicated thereafter.
 
It is 150 mg of combined EPA and DHA per kg body weight to be given either as a single or divided into smaller doses through the day.
		
	
Vitamin-D 25OH (Cholecalciferol)
	
Based on the Vitamin D level and age of the participant
 
For levels 30 -39 ng/ml:
 
Age ≤10 years give 500 IU daily
 
Age >10 years give 1000 IU daily
 
For levels 20 – 29 ng/ml
 
50,000 IU weekly for 2 months and then:
 
Age ≤10 years give 1000 IU daily
 
Age >10 years give 2000 IU daily
 
For levels < 20 ng/ml
	
Daily orally
	
Daily orally

		
50,000 IU weekly for 6 months and then:
 
Age ≤10 years, give 1000 IU daily
 
Age >10 years, give 2000 IU daily
 
Dose will be adjusted and monitored every four months until achieving target levels and as clinically indicated thereafter.
		
Treatment Description	Subjects will be randomized to one of the two arms. The treatment arm A includes Omega-3 Fatty Acids and Vitamin D. The subjects randomized in Arm B (control group) will receive only Vitamin D supplement. The treatment assignment will be conducted in a open label fashion.			

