5.4.2.1. Vitamin D Administration

Vitamin D supplementation

1. For levels of Vitamin D 25OH of 30 -39 ng/ml:
 - a. age ≤10 years give 500 IU daily
 - b. age >10 years give 1000 IU daily
2. For levels of Vitamin D 25OH of 20 – 29 ng/ml give 50,000 IU weekly for 2 months and then:
 - a. age ≤10 years give 1000 IU daily
 - b. age >10 years give 2000 IU daily
3. For levels of Vitamin D 25OH of < 20 ng/ml give 50,000 IU weekly for 4 months and then:
 - a. age ≤10 years give 1000 IU daily

- b. age >10 years 2000 IU daily

Repeat vitamin D 25OH levels 1 week after the last 50,000 IU dose:

- For children whose levels are not above 30 ng/ml on repeat testing, repeat treatment as above.
- For children whose levels are 30 -39 ng/ml on repeat testing:
 - if age ≤10 years increase vitamin D supplementation to 1000 IU daily
 - if age is >10 years give 2000 IU daily

Thereafter, monitor vitamin D 25OH levels every 4 months (or more frequently at the discretion of the investigator) and adjust Vitamin D treatment to maintain levels > 40 ng/ml.

Study participants with or without a history of vitamin D deficiency who are on vitamin D replacement will continue their current dose if 25OH vitamin D levels checked at screening are in line with study targets. This may defer from the doses indicated above which apply to participants who are not on vitamin D replacement. Doses will then be adjusted at the discretion of the Principal Investigator in order to maintain 25OH vitamin D levels >40 ng/mL.

The Dietary Reference Intake Committee to Review Dietary Reference Intakes for Vitamin D and Calcium from Institutie of Medicine, recommends following upper intake levels for Vitamin D (see page 403-477)(https://www.ncbi.nlm.nih.gov/books/NBK56070/pdf/Bookshelf_NBK56070.pdf)

Table Representing Tolerable Upper Intake Levels (ULs) for Vitamin D				
Age	Male	Female	Pregnancy	Lactation
0–6 months	1,000 IU (25 mcg)	1,000 IU (25 mcg)		
7–12 months	1,500 IU (38 mcg)	1,500 IU (38 mcg)		
1–3 years	2,500 IU (63 mcg)	2,500 IU (63 mcg)		
4–8 years	3,000 IU (75 mcg)	3,000 IU (75 mcg)		
≥9 years	4,000 IU (100 mcg)	4,000 IU (100 mcg)	4,000 IU (100 mcg)	4,000 IU (100 mcg)

Microcrystalline cellulose is the only excipient in Biotech Pharmacal Vitamin D3 capsule with following quantities:

- D3-5000 IU capsule contains 89 mg of microcrystalline cellulose
- D3-1000 IU capsule contains 92.8 mg of microcrystalline cellulose
- D3 50,000 IU capsule contains 115 mg of microcrystalline cellulose

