5.4.2.2. Modification or Discontinuation of Vitamin D

Vitamin D is likely safe when taken by mouth in recommended amounts. Most people do not commonly experience side effects with vitamin D, unless too much is taken. Some side effects of excess vitamin D include weakness, fatigue, sleepiness, headache, loss of appetite, dry mouth, metallic taste, nausea, and vomiting.

Taking vitamin D for long periods of time in doses higher than 4000 units daily is possibly unsafe and may cause excessively high levels of calcium in the blood. However, much higher doses are often needed for the short-term treatment of vitamin D deficiency.

Vitamin D in very high doses can make the intestines absorb too much calcium which can cause high levels of calcium in the blood (hypercalcemia). This can cause side effects including nausea, vomiting, constipation, poor appetite, weakness, weight loss, confusion and disorientation. Hypercalcemia can also lead to kidney stones, damage to the kidneys, and cause calcium deposits in heart and lungs. We will monitor blood levels of vitamin D to minimize the risk of these side-effects.

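### For 25OH vitamin D below 20 ng/ml, weekly 50,000 IU loading lasts 6 months in synopsis Table 1 but 4 months in section 5.4.2.1, and nothing says which governs

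*Combined protocol and SAP*

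**What the plan says.** Two current parts of the protocol set the vitamin D regimen by baseline level and age.

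- **Section 1.1, Table 1, band below 20 ng/ml:** "50,000 IU weekly for 6 months and then" 1000 IU daily at age 10 or under, or 2000 IU daily above age 10. Beneath the bands the table adds: "Dose will be adjusted and monitored every four months until achieving target levels and as clinically indicated thereafter".
- **Section 5.4.2.1, item 3, same band:** "give 50,000 IU weekly for 4 months and then" the same 1000 or 2000 IU daily by age.

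Section 5.4.2.1 then adds a recheck, "Repeat vitamin D 25OH levels 1 week after the last 50,000 IU dose", and a branch: "For children whose levels are not above 30 ng/ml on repeat testing, repeat treatment as above". It says that the listed doses "apply to participants who are not on vitamin D replacement". Later monitoring is four-monthly, or more often at the investigator's discretion, and footnote 4 of the schedule of events (Appendix A) says the same.

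**The concern.** This is a study-drug instruction with two different values. Drug is dispensed at visits 1, 2 and 3. Around visit 2 (day 120), one text moves the participant to daily maintenance and the other continues 50,000 IU weekly for about two more months. Two members of staff, each following a valid page of the protocol, could treat the same participant differently. That participant may be a child.

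The protocol's own caution depends on duration. Section 5.4.2.2 states: "Taking vitamin D for long periods of time in doses higher than 4000 units daily is possibly unsafe". It accepts much larger amounts for brief correction of deficiency, but it puts no length on either the long or the brief period. The disputed two months are therefore the part of the course that this caution leaves unclassified.

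The trial sets out to assess the safety and feasibility of high-dose cholecalciferol, and vitamin D alone is the control regimen. As written, that regimen is not uniquely defined for this band.

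**Working it through.** **1. Is it the same rule in both places?**

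| 25OH vitamin D | Section 1.1, Table 1 | Section 5.4.2.1 |
|---|---|---|
| 30-39 ng/ml | 500 / 1000 IU daily by age | same |
| 20-29 ng/ml | 50,000 IU weekly, 2 months, then 1000 / 2000 IU daily | same |
| below 20 ng/ml | 50,000 IU weekly, **6 months**, then 1000 / 2000 IU daily | 50,000 IU weekly, **4 months**, then 1000 / 2000 IU daily |

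The 6-month line comes directly after the heading for the band below 20 ng/ml and carries the same follow-on doses as item 3. The match of band to band is therefore secure, and the difference does not come from a broken table. Neither text is in a log of changes.

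**2. Does any other text decide between them?** No. The recheck is tied to the last loading dose, so it depends on the disputed duration. The four-monthly adjustment in Table 1, the later monitoring in section 5.4.2.1 and footnote 4 of Appendix A govern testing and titration, not the length of the first course. The Principal Investigator's discretion in section 5.4.2.1 follows the text on participants already on replacement. Section 11 says that dosage depends on blood levels but gives no duration.

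**3. Nominal dose difference over six months.** The loading duration is a stated rule, so there is no derived figure to reproduce. Assume a month of 365.25/12 = 30.4375 days, no level-based adjustment, and maintenance in months 5-6 under the 4-month text.

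- 4 months = 121.75 days = 17.39 weeks; 6 months = 182.625 days = 26.09 weeks; months 5-6 = 60.875 days.
- 6-month text: 26.09 weeks × 50,000 = 1,304,464 IU (unrounded weeks).
- 4-month text, loading: 17.39 weeks × 50,000 = 869,643 IU.
- Age 10 or under: 869,643 + 60.875 × 1000 = 930,518 IU. Difference 373,946 IU; ratio 1.40.
- Above age 10: 869,643 + 60.875 × 2000 = 991,393 IU. Difference 313,071 IU; ratio 1.32.

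Other counting conventions:

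| Weekly doses | Maintenance days | Age 10 or under | Above age 10 |
|---|---|---|---|
| 16 v 24 (4-week months) | 56 | 344,000 (1.40) | 288,000 (1.32) |
| 17 v 26 | 63 | 387,000 (1.42) | 324,000 (1.33) |
| 17 v 26 | 60.875 | 389,125 (1.43) | 328,250 (1.34) |
| 18 v 27 (both end days counted) | 63 | 387,000 (1.40) | 324,000 (1.32) |

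**4. Average daily amount in months 5-6.** 50,000/7 = 7,143 IU under the 6-month text, against 1000 or 2000 IU under the 4-month text. These lie on opposite sides of the 4000-unit figure in section 5.4.2.2.

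**5. Timing of the recheck.** The first dose is due within 48 hours of baseline, so take a start on day 1 to 3. With n weekly doses the recheck falls on start + 7n.

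- 4 months, n = 16 to 18: days 113-129, inside the visit 2 window (120 ± 14 = days 106-134).
- 6 months, n = 24 to 27: days 169-192, outside any visit window.
- Shift: 8 to 9 weeks, or 56 to 63 days.
- Undisputed 2-month band, n = 8 or 9: days 57-66, also outside any window.

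**The case against.** The contradiction itself cannot be disputed. The strongest reply is that it matters less than the totals suggest.

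- **The repeat branch.** A child not above 30 ng/ml at recheck goes back to weekly loading under the 4-month text as well. With 17 doses from day 1, the last dose is on day 113 and the recheck on day 120. Section 11 allows up to a week for the result, so dosing resumes between day 120 and day 127. By day 176 the child has had 25 or 26 doses, against 26 under the 6-month text. This stands: the differences in IU apply only to participants who move to maintenance. The branch is worded for children only.
- **Visit 2 as a control.** A vitamin D level, dispensing and a count of returned drug are all scheduled at visit 2, so dosing in month 5 can be reviewed against a fresh level under either text. This also stands for actual exposure. It does not say which course the participant was meant to be on.
- **The recheck shift.** The one-week rule appears only in section 5.4.2.1, so the shift comes from applying that rule to Table 1's duration. The draw can also be made off-visit, as the 2-month band already requires. This point is fair, and the shift is secondary.
- **Safety and setting.** Both texts average more than 4000 IU daily for at least four months, and the trial runs within one university with one research pharmacy. Harm is not shown, and divergent dosing is a possibility rather than an observed fact.

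These points reduce the size of the consequence. None of them supplies the missing rule.

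**Conclusion.** The concern holds. For the band below 20 ng/ml, two current texts give different loading durations for the same weekly dose, and the document does not say which governs. The case for correcting it rests on its being an unresolved study-drug rule that covers adults and children, not on the calculated gap in exposure.

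The nominal size is about 17 against 26 weekly doses. Over six months, net of maintenance, the difference is about 374,000 IU at age 10 or under (344,000 to 389,000 across counting conventions) and about 313,000 IU above age 10 (288,000 to 328,000). These figures assume no level-based adjustment and a move to maintenance after 4 months under the shorter text. For a child whose level stays low, the six-month gap is about 0 to 1 dose. The documents do not give the number of participants in this band.

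Both arms are affected alike, so the conflict alone does not bias the treatment comparison. It is not evidence that either duration is unsafe.

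**What to change.** Reconcile Table 1 in section 1.1 with item 3 of section 5.4.2.1, so that both give one loading duration chosen by the sponsor's clinicians. This review takes no view on which duration that should be. If any participant in this band has already been dosed, establish from the dispensing records which version was used.

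The cost is a wording correction or minor amendment, plus the records check where it applies. Sample size and alpha do not change.

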5.4.2.2. Modification or Discontinuation of Vitamin D

Vitamin D is likely safe when taken by mouth in recommended amounts. Most people do not commonly experience side effects with vitamin D, unless too much is taken. Some side effects of excess vitamin D include weakness, fatigue, sleepiness, headache, loss of appetite, dry mouth, metallic taste, nausea, and vomiting.

Taking vitamin D for long periods of time in doses higher than 4000 units daily is possibly unsafe and may cause excessively high levels of calcium in the blood. However, much higher doses are often needed for the short-term treatment of vitamin D deficiency.

Vitamin D in very high doses can make the intestines absorb too much calcium which can cause high levels of calcium in the blood (hypercalcemia). This can cause side effects including nausea, vomiting, constipation, poor appetite, weakness, weight loss, confusion and disorientation. Hypercalcemia can also lead to kidney stones, damage to the kidneys, and cause calcium deposits in heart and lungs. We will monitor blood levels of vitamin D to minimize the risk of these side-effects.

5.4.2.3. Contraindications for Vitamin D Supplement

There are conditions where Vitamin D treatment require special precautions and these subjects will not be included in this study:

Kidney disease: Vitamin D may increase calcium levels and increase the risk of arteriosclerosis" in people with serious kidney disease. This must be balanced with the need to prevent renal osteodystrophy, a bone disease that occurs when the kidneys fail to maintain the proper levels of calcium and phosphorus in the blood.

Sarcoidosis: Vitamin D may increase calcium levels in people with sarcoidosis. This could lead to kidney stones and other problems..

Histoplasmosis: Vitamin D may increase calcium levels in people with histoplasmosis. This could lead to kidney stones and other problems..

Over-active parathyroid gland (hyperparathyroidism): Vitamin D may increase calcium levels in people with hyperparathyroidism..

Lymphoma: Vitamin D may increase calcium levels in people with lymphoma. This could lead to kidney stones and other problems..

Tuberculosis: Vitamin D might increase calcium levels in people with tuberculosis. This might result in complications such as kidney stones.

5.4.3. Assessment of Participant Compliance with Study Agent

Patients will be closely monitored to assess compliance of study drug administration. Each participant will return the empty bottles to the Coordinator to assess compliance, which in turn will be returned to the Pharmacy for appropriate on-site destruction and for documentation purposes.

5.4.4. Prior and Concomitant Treatments

The use of concomitant medications will be assessed at each study visit and recorded on an appropriate source document and CRF. Participants are allowed to use preparations of insulin as advised by the investigator or the referring physician.

The following medications are prohibited during participation in this study:

- Agents that influence insulin sensitivity or secretion (e.g. pramlintide, sulfonylureas, metformin, diphenylhydantoin, thiazide, or other potassium-depleting diuretics, beta-adrenergic blockers, niacin etc).

If participants receive, or if the investigator believes that participants must receive, any of the above medications, the case must be immediately discussed with the medical monitor. The use of prohibited medications must be documented on the source document and CRF, and a protocol deviation must be requested. A decision regarding continuation of the participant in the trial will be made by the study PI, and the medical monitor.

5.4.5. Removal of Subjects from Therapy or Subject Withdrawal or Early Termination

- **Withdrawal of consent** - Participants who withdraw consent will be asked to complete all the assessments listed for the end of treatment follow-up
- **Failure to return** - Participants who do not return for visits and who do not respond to repeated attempts by the site staff to have them return will be considered lost to follow-up.
- **Investigator judgment** - A severe or serious AE occurs, which, based on the medical judgment of the investigator, prevents completion of participation in the study.

5.4.6. Discontinuation of study drug(s) in an individual patient

The dosing and administration of investigational medication according to study specification will be discontinued for an individual participant if any of the following criteria is met:

- Subjects who have 3 severe hypoglycemic reactions on separate days (requiring assistance from another individual)
- Subjects who have nausea or vomiting that precludes adherence to diet will discontinue the use of the study drug.
- Subjects who lose more than 10 kg in weight from baseline.

- Any grade 3 or higher AE occurs that, based on the medical judgment of the investigator, the medical monitor, and the clinical trial physician, prevents completion of the course of study treatment.
- Any unexpected, treatment-related SAE resulting in permanent treatment discontinuation and not related to glycemic events.
- The investigator determines that it is in the participant's best interest to discontinue treatment.
- The participant, or participant's legal representative, requests that treatment be halted.
- The participant becomes pregnant.

Further care will be provided according to the judgment and practice of the investigator. The participant will be asked to remain in the study and participate in follow-up. If study treatment is discontinued, the medical monitor will be notified. Participants who prematurely terminate from the study will not be replaced.

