5.4.1.1. Ultra-refined omega-3 EPA/DHA concentrate (ZoneLabs® OmegaRx®2 Fish Oil) Administration

Participants will receive ultra-refined omega-3 EPA/DHA concentrate (ZoneLabs® OmegaRx®2 Fish Oil – Liquid; containing 3375 mg EPA+DHA [2250 mg EPA and 1125 mg DHA] in 5 mL).

Research subjects will be started at a dose of 150 mg of EPA+DHA per Kg body weight.

For example:

- The dose for a 22.5 Kg child will be:
 $150 \text{ mg} \times 22.5 \text{ Kg} = 3375 \text{ mg}$ of EPA+DHA fish oil corresponding to 5 mL of Omega Rx ®2 Fish Oil Liquid.
- The dose for a 30 Kg child will be:
 $150 \text{ mg} \times 30 \text{ Kg} = 4500 \text{ mg}$ of EPA+DHA fish oil corresponding to 6.7 mL of Omega Rx ®2 Fish Oil Liquid.

Participants who are unable to tolerate the liquid formulation will be switched to the OmegaRx®2 capsule formulation at the same dose as described above.

It is 150 mg of combined EPA and DHA per kg body weight to be given either as a single or divided into smaller doses through the day.

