5.4.1.3. Discontinuation of omega-3 EPA/DHA concentrate

Subjects would be continuously evaluated for any untoward effects of Omega-3 fatty acid supplements or negative side effects. Typically side effects consist of minor gastrointestinal symptoms, such as belching, indigestion, or diarrhea, stomach pain or discomfort, burping, heartburn, vomiting, constipation, nausea, and change in the sense of taste. Joint pain may be a side effect as well.

Patients with coagulation, bleeding, or blood disorders will be excluded. We will monitor clotting times of enrolled subjects by measuring the prothrombin time (PT/PT-INR) during all subject visits (except for visit 1), in addition to CBC with differentials (see schedule of assessment).

Symptomatic management of the side effects will be evaluated by the study physician and should the investigator believes that the study treatment is no longer in the best interest of the participant, subjects would be discontinued from the treatment. Similarly, if subject begins taking medications that affect clotting chronically, subjects would be discontinued and appropriately noted in the study record. Participants who prematurely discontinue study treatment will remain in the study and undergo all efficacy and safety assessments.

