5.4.8. Risk to the Subjects

The risks of these over the counter drugs is summarize below:

- Omega-3 Fatty Acids may cause gastrointestinal side- effects including stomach pain or discomfort, burping, heartburn, vomiting, constipation, diarrhea, nausea, and change in the sense of taste. Joint pain may be a side effect as well.
- Vitamin D in very high doses can make the intestines absorb too much calcium which can cause high levels of calcium in the blood (hypercalcemia). This can cause side effects including nausea, vomiting, constipation, poor appetite, weakness, weight loss, confusion and disorientation. Hypercalcemia can also lead to kidney stones, damage to the kidneys, and cause calcium deposits in heart and lungs. We will monitor blood levels to minimize these risks.

Allergic reaction: As with any drug, it is possible that subjects could experience an allergic reaction to OMEGA-3, or Vitamin D. Such allergic reactions include: itching, skin rash, sudden drop in blood pressure, loss of consciousness and/or associated with seizures, including the possibility of death.

Blood draw risks: Drawing blood may cause temporary pain from the needle stick, bruising or swelling at the site, and rarely, infection or fainting.

Hypoglycemia: These medications could lower blood sugar too much (hypoglycemia). This could make subjects feel tired, dizzy, sweaty, and/or nauseated. Also, it could cause heart to feel as if it is racing. There may also be other effects. Untreated hypoglycemia could cause convulsions, loss of consciousness, and can lead to death. The clinical research team will provide added training and education to subjects to better manage hypoglycemia and other diabetes related complications.

Unknown Risks: The experimental drug may have side effects that no one knows about yet. The researchers will let you know if they learn anything that might make you change your mind about participating in the study.

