6.11. Staggering Administration

Please note that the enrollment of patients in this trial is staggered across individuals. Initially, a total of 6 subjects will be randomized in each of the following groups:

Group	Subject population
I	Fourteen (14) adults (18-65 years) of established T1D of more than 6 months duration (>180 days) and up to 10 years
II	Fourteen (14) adults (18-65 years) of new-onset T1D diagnosed within last 6 months (\leq 180 days)
III	Fourteen (14) children (6-17 years) of established T1D of more than 6 months duration (>180 days) and up to 10 years
IV	Fourteen (14) children (6-17 years) of new-onset T1D diagnosed within last 6 months (\leq 180 days)

All 24 subjects will be monitored for acute and subacute adverse events for 90 days and a formal DSMB (Data and Safety Monitoring Board) will review the data and safety prior to treating additional subjects. This will limit the number of subjects who might be exposed to any unanticipated safety risk.

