6.16. Stopping rules

As stated earlier, the progress of the study will be monitored by the DSMB which will review safety data and make recommendations regarding continuation, termination, or modification of the study. Based on a 12 month enrollment period and an additional study period of 12 months, the DSMB will formally review the safety data after participant number 24 reaches day 90 of the study. The number of subjects who discontinue study treatment will also be included in the reports prepared for the DSMB.

In addition, safety data will be reviewed by the DSMB when an event occurs that is of sufficient concern to the medical monitor and/or study investigator(s) to warrant review, or when an event occurs that contributes to a stopping rule listed below.

- **Patient stopping rules:** Subjects who have 3 severe hypoglycemic reactions (requiring assistance from another individual) on separate days or who have nausea or vomiting that precludes adherence to diet will discontinue the use of the study drug. Subjects who lose more than 10 kg will also discontinue study drug. Subjects who discontinue the drug treatment will not be replaced.
- **Trial stopping rules:** Interim analysis will be conducted when recommended by the DSMB to review safety data, including metabolic, immunological assessments and adverse events. The DSMB may recommend early stopping if there is sufficient evidence to conclude that the investigational treatment is harmful based on interim analysis of safety endpoints.

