7. ADVERSE EVENT REPORTING AND SAFETY MONITORING

7.1. Adverse Event Definition

7.1.1. Adverse Event (AE)

In this clinical study, an adverse event is any occurrence or worsening of an undesirable or unintended sign, symptom or disease whether or not associated with the treatment and study procedures.

Throughout the study, the investigator must record all adverse events on source documents. Events not related to hypo or hyperglycemia that are Grade 2 or greater per the NCI CTCAE (see Grading Event Severity below) will be reviewed by study physician and medical monitor on the appropriate adverse event form. The investigator will treat participants with adverse events appropriately and observe them at suitable intervals until the events resolve or stabilize.

Adverse events may be discovered through:

- observation of the participant;
- questioning the participant;
- unsolicited complaint by the participant

In questioning the participant the questioning should be conducted in an objective manner.

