§ Mechanistic Assessments: includes samples for RNA, plasma, serum, DNA, measures of B and T cell number/function and cytokine profiles. The schedule for these assessments may vary as appropriate. At no time will the blood draw volume exceed what is allowable according to the subject's body weight.

Mechanistic Samples (total volume: 21 ml) as follows:

Pro-inflammatory cytokines: 3.5 mL
 Phenotyping: 2 mL
 RNA: 2.5 mL
 DNA: 2.5 mL
 Resolvins: 2 mL
 LPS activation T-cell stimulation assay: 3 mL
 Plasma: 2 mL
 Serum: 3.5 mL

*Stimulated c-peptide at 90 min is a time point of the MMTT. No extra sample collection needed.

- **Ages 6 to <18 y/o**
- **Weight at screening visit (Kg): 17 to < 19**

Maximum Draw Allowed Per Day (5mL/Kg): 85 mL/kg

Maximum Draw Allowed Per 8 Week Period (9.5 mL/Kg): 162 mL

Visit number	0	1	2	3	4	5 F1	6 F2	7 F3
Days of the trial	-1	1	120	240	360	480	600	720
Months	1	1	4	8	12	16	20	24
CBC with differential	2 mL	2 mL	2 mL	2 mL	2 mL			
Prothrombin time (PT/PT-INR)	1.8 mL		1.8 mL					
Chemistries	3.5 mL		3.5 mL	3.5 mL	3.5 mL			
Pregnancy test ¥	¥		¥	¥	¥	3.5 mL		
Serum for islet autoantibodies	3.5 mL		3.5 mL					
Serology	3.5 mL							
Mechanistic assessments §		21 mL	21 mL	21 mL	21 mL	21 mL	21 mL	21 mL
Hemoglobin A1c	2 mL		2 mL					
Simulated C-peptide at 90 min*	X				X			X
MMTT 4 hour	38.5 mL				38.5 mL			
Vitamin D levels	3.5 mL		3.5 mL					
AA/EPA Ratio	2 mL		2 mL					
Total Blood collection per visit	60.3 mL	23 mL	39.3 mL	39.3 mL	77.8 mL	37.3 mL	33.8 mL	33.8 mL

¥ Pregnancy test for visits -1; 120; 240, and 360 will be performed using same serum sample for chemistry. For visit 480 a 3.5 mL SST tube (serum sample) will be collected to perform the test in the absence of a chemistry sample requirement

§ Mechanistic Assessments: includes samples for RNA, plasma, serum, DNA, measures of B and T cell number/function and cytokine profiles. The schedule for these assessments may vary as appropriate. At no time will the blood draw volume exceed what is allowable according to the subject's body weight.

Mechanistic Samples (total volume: 21 ml) as follows:

Pro-inflammatory cytokines: 3.5 ml
 Phenotyping: 2 mL
 RNA: 2.5 mL
 DNA: 2.5 mL
 Resolvens: 2 mL
 LPS activation T-cell stimulation assay: 3 mL
 Plasma: 2 mL
 Serum: 3.5 mL

*Stimulated c-peptide at 90 min is a time point of the MMTT. No extra sample collection needed.

- Ages 6 to <18 y/o
- Weight at screening visit (Kg): 16 to < 17

Maximum Draw Allowed Per Day (5mL/Kg): 80 mL/kg

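### The 10 kg weight-loss rule for stopping study drug is not scaled to body size, so it gives light children no working objective trigger

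*Combined protocol and SAP*

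**What the plan says.** Section 5.4.6 lists the criteria that end dosing for an individual participant. Meeting any one is enough. The weight criterion reads "Subjects who lose more than 10 kg in weight from baseline". Section 6.16 repeats it among the patient stopping rules: "Subjects who lose more than 10 kg will also discontinue study drug". Neither section gives a percentage or a version for children, no other section does, and no reason is given for the figure of 10 kg.

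The rule covers ages 6 to 65 (4.4.1). Two of the four groups are children; group IV, for example, is "Fourteen (14) children (6-17 years) of new-onset T1D diagnosed within last 6 months". The dosing section works an example that begins "The dose for a 22.5 Kg child will be" and a second at 30 kg (5.4.1.1). The lightest blood-draw table in Appendix B is headed "Weight at screening visit (Kg): 16 to < 17".

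Other provisions also bear on a child who loses weight:

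- On omega-3, section 5.4.1.3 says: "Subjects would be continuously evaluated for any untoward effects of Omega-3 fatty acid supplements or negative side effects".
- Section 7.1.1 provides that non-glycemic events of "Grade 2 or greater per the NCI CTCAE (see Grading Event Severity below) will be reviewed by study physician and medical monitor".
- Section 7.1.13 makes a significant deterioration found at an interim or final physical examination recordable as an adverse event. Section 6.1 includes weight loss in that examination.

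**The concern.** The protocol made weight loss a mandatory, numeric reason to stop study drug. An absolute limit in kilograms means very different things at different body sizes. A loss that would be serious in a small child can fall far short of it.

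Other quantities in the protocol are scaled to weight: the omega-3 dose (150 mg/kg), the test meal (6 mL/kg up to a cap, section 4.8) and the pediatric blood-draw limits (5 mL/kg per day, Appendix B). The stopping rule is not.

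Section 5.4.8 gives some clinical relevance. On hypercalcemia from very high vitamin D doses it says: "This can cause side effects including nausea, vomiting, constipation, poor appetite, weakness, weight loss, confusion and disorientation". Both arms take vitamin D, although its blood levels are monitored to limit that risk. What is at stake is one objective trigger for one subgroup: in a light child, stopping for weight loss depends on symptoms, on how an examination finding is recorded and graded, or on judgment.

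**Working it through.** **Inputs.** The threshold is a loss of more than 10 kg (5.4.6, 6.16). The child weights are 22.5 kg and 30 kg (5.4.1.1), and the lower edge of the lightest band is 16 kg (Appendix B). The adult weights of 60 kg and 70 kg are assumptions, for comparison only.

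**Can the plan's figure be reproduced?** The 10 kg limit has no stated derivation, so there is nothing to reproduce. The weight-scaled figures elsewhere do reproduce:

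- Dose: 150 × 22.5 = 3375 mg, and 3375 / 675 = 5 mL; 150 × 30 = 4500 mg, and 4500 / 675 = 6.7 mL.
- Daily blood-draw limit: 5 × 16 = 80 mL.

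**Loss needed to meet the rule.** Formula: 10 / baseline weight × 100. The rule says *more than* 10 kg, so the required loss lies above each figure.

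| Baseline weight | Source | 10 kg as % of baseline | Weight left after losing 10 kg |
|---|---|---|---|
| 16 kg | Appendix B, lightest band | 62.5% | 6 kg |
| 22.5 kg | 5.4.1.1 example | 44.4% | 12.5 kg |
| 30 kg | 5.4.1.1 example | 33.3% | 20 kg |
| 50 kg | 10 / 0.20 | 20.0% | 40 kg |
| 60 kg | assumed | 16.7% | 50 kg |
| 70 kg | assumed | 14.3% | 60 kg |

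Below 50 kg the rule always needs more than 20%. For instance, a 22.5 kg child who lost 5 kg (5 / 22.5 = 22.2%) would not meet it.

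**When could the rule act?** Treatment lasts one year. Appendix A shows drug dispensed at visits 1, 2 and 3, and physical examinations during treatment at months 4, 8 and 12. By month 12 no treatment remains to be stopped, so the useful scheduled checks are months 4 and 8. (A footnote calls the examinations quarterly; the grid shows them every four months, and the grid is used here.)

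**Who is affected?** Children number 14 + 14 = 28 of 56. How many of them are light cannot be computed, because the documents give no weight distribution.

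**The case against.** The strongest reply is that a light child is not left without protection. Section 5.4.6 also stops drug for:

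- nausea or vomiting that prevents keeping to the diet;
- three severe hypoglycemic reactions on separate days;
- a grade 3 or higher adverse event, on medical judgment;
- an unexpected treatment-related serious adverse event that leads to permanent discontinuation;
- the investigator's decision;
- a request from the participant or legal representative.

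Under section 7.1.13, an examination finding alone can be recorded as an adverse event, even without symptoms. It can then reach grade 2 review (7.1.1) and the DSMB's regular reviews by treatment group (7.1.6). All of this stands, and it narrows the gap. It does not close it, because none of these routes states a weight threshold. The CTCAE table is reproduced only for hypoglycemia, so how it would grade weight loss cannot be checked here.

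It can also be objected that the protocol explicitly records body weight only at screening (6.3), that Appendix A has no row for weight, and that remote visits are encouraged (5.4 and section 6). That is fair, but it applies equally to the existing rule, which cannot be enforced without follow-up weights.

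A reader might infer more than the documents support:

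- *Half the trial is affected.* The figure of 28 of 56 counts everyone aged 6 to 17. A heavier adolescent meets the rule at the same percentage as an adult of that weight.
- *Children of 16 kg are expected.* Appendix B shows the lowest weight provided for, not the weights that will be enrolled.
- *The rule was written for hypercalcemia, or omega-3 is expected to cause weight loss.* No purpose is given for the rule, and weight loss is not in the listed omega-3 side effects (5.4.1.3, 5.4.8).

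**Conclusion.** The concern holds in a limited form. As written, the weight rule does not work as an objective trigger for light children: it needs more than 44% at 22.5 kg, more than 33% at 30 kg, and more than 20% in anyone under 50 kg. These figures use only the protocol's threshold and simple division. Calling such losses too large for a useful trigger is a clinical judgment, but at the protocol's own example weights it is hardly in doubt.

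The documents do not support saying that light children have no safeguard, or that the rule fails adults. The size of the affected group is unknown. The primary endpoint, alpha and power are affected negligibly. This is a safety-wording point of minor-to-moderate priority.

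**What to change.** In both 5.4.6 and 6.16, write: *loss of more than 10 kg or, for participants under 18, more than X% of baseline (screening) weight, whichever is smaller*. Adults are then unchanged. The sponsor's clinicians and the medical monitor set X, at no more than 20%; that ceiling is an assumption, not a figure from the documents. At X = 20% the trigger is a loss above 0.20 × 22.5 = 4.5 kg or 0.20 × 30 = 6.0 kg, and nothing changes at 50 kg or above (0.20 × 50 = 10 kg). The 22.5 kg child who lost 5 kg would then meet the rule. Because the limit still counts from a fixed baseline, it makes no allowance for growth during the year; this is a reason to consider a lower X.

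Also state that body weight is recorded at the month 4 and month 8 visits, with a home weight if the visit is remote. The existing rule already needs this.

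The cost is wording in two sections and an explicit weight entry at two visits. The downside is that a few light children may stop drug earlier. They are asked to remain in follow-up (5.4.6), stay in the intention-to-treat analysis (5.4.7) and are not replaced (6.16), so the treatment contrast could be slightly diluted. A worst-case bound assumes that a combination-arm child who stops loses the whole planned effect (50% against 5%, section 9.7; 28 per arm, section 4.6). Each such child then lowers the expected combination-arm proportion by (50 − 5) / 28 = 1.6 percentage points.
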